5.1. Study Setting

816 The sites for the SMART trial will include four (4) youth mental health services (headspace 817 centres) funded through the Commonwealth Government of Australia. These centres, 818 located in purpose-built premises in shopping and community precincts in the suburbs of 819 Sunshine, Glenroy, Werribee and Craigieburn, in the North Western Melbourne 820 metropolitan region, provide universal access under a Federally-funded model of enhanced 821 primary care, to a broad array of mental health and welfare services for 12-25 year olds 822 (inclusive) in a youth friendly, stigma-free "one stop shop" environment. These headspace 823 recruitment sites are operated under contract to headspace nationally by Orygen of which 824 the Principal Investigator [name] is Executive Director, and they have already been the 825 platform for several successful clinical trials and cohort studies. From 2014, over 5000 young 826 people will be seen at these 4 clinics per annum. The study will also recruit from the PACE 827 clinic, a specialised UHR research clinic that has two decades of innovation, clinical and 828 research experience with this group of patients and their families (22, 134, 142).

5.2. Study Endpoints

5.2.1. Primary Endpoint

The primary endpoint is 6 months post-baseline (end of Step 2). The study will test the effect of the sequential treatment approach of SPS and CBCM on functioning levels at this time point. Functioning will be measured using the Global Functioning: Social and Role Scales (135).

837

835 **5.2.2. Secondary Endpoint(s)**

- Functioning levels 12 months from baseline (end of Step 3), as measured using the Global Functioning: Social and Role Scales.
- Transition to psychotic disorder by 12 months and 24 months from baseline, as assessed using the CAARMS (142).
- UHR status (maintenance versus remission) 1.5 months, 6 months, 12 and 24 months into treatment as determined by the CAARMS.
- Psychiatric symptomatology, including positive psychotic symptoms, negative psychotic
 symptoms and depressive symptoms 1.5 months, 6 months, 12 months and 24 months
 into treatment assessed using the CAARMS, BPRS, SANS and MADRS.
- Relapse rates (i.e., relapse to UHR+ status) in the relapse prevention/responder arm of the trial (SPS v monitoring) during the first 12 months.

847 **5.3. Study Duration**

- The controlled intervention component of the study is of 12 months duration. Participants
- will be followed up with research assessments up to 24 months post-baseline.

850 **5.4. Study Risk Assessment**

- Participants in the active treatment arm of the study will have regular (ideally weekly-
- 852 fortnightly) contact with their treating team (case managers and/or psychiatrist), during
- 853 which risk will be monitored. Participants in the non-active treatment arm will either have
- 854 monthly contact with their treating team or undergo 3-monthly monitoring. If participants
- are deemed to be at substantial risk to themselves or others (see definition in 9.8.2) they will
- 856 be discontinued from the study and receive required clinical care. These participants will
- continue to be followed up with research assessments.

6. Participant Population

6.1. Description

858

- 860 Male and female participants aged between 12 and 25 (inclusive) who meet "ultra high risk"
- 861 for psychosis criteria at entry to services as determined using the CAARMS.

862 6.2. Sample Size and Power

- 863 The study is powered on the primary aim of comparing six-month functional outcome
- between the two treatment groups in Step 2. Previous data collected at the PACE clinic
- 865 indicates that approximately 50% of UHR participants remain UHR+ 6 weeks into treatment
- 866 (i.e., will be classified as "non-responders" to Step 1 intervention). Assuming a 50% non-
- response rate in Step 1, an entry sample size of 500, a drop-out rate of 20% and hence a step

868	2 sample size of 200, we will be able to detect a fairly small effect size (0.18 in a parallel cell
869	design) with a power of 80% and significance level of .05 by the end of Step 2. Approximately
870	5000 young people per annum will be attending headspace centres from 2014. Recent data
871	indicates that approximately 38% of young people seen at headspace meet UHR criteria,
872	which means that approximately 2000 patients per annum will be eligible for the study. A
873	two-year recruitment period means that 500 participants would need to be recruited from a
874	pool of 4000 patients (12.5%). This recruitment rate is highly realistic given that recruitment
875	rates to our previous UHR intervention trials have been approximately 30% of eligible
876	patients (143). It is standard for SMART trials to be powered on a single stage or aspect of a
877	multi-staged design (127). Nevertheless, assuming 50% non-response rate in Step 2 and 20%
878	drop-out rate will result in n=80 in Step 3 which will be sufficient to detect a clinically
879	important medium effect size (0.29) for comparing the two interventions with a power of
880	80% and significance level of .05.

881 6.3. Participant Selection Record

882 Investigators are to keep a record of participants who were screened for the study but were

883 not enrolled.

891

892

893

894

895

896 897

898

899

900

901

884 6.4. General Considerations for Enrolment

- 885 Only participants who meet all of the inclusion and none of the exclusion criteria will be
- 886 eligible to participate in the study. Applications for individual protocol waivers will be
- 887 considered on a case-by-case basis.

888 6.5. Inclusion Criteria

A participant will be considered eligible for inclusion in this study only if all of the following criteria apply:

- 1. Age 12 25 years (inclusive) at entry
- 2. Ability to speak adequate English (for assessment purposes)
- 3. Ability to provide informed consent. Where participants are minors (i.e. have not reached the age of eighteen), consent will also be obtained from one of the participant's parents or legal guardian. Both the parent/legal guardian and participant will be required to sign a consent form in such a case. It will be the treating doctor's decision made in consultation with the investigator to determine whether a participant who is a mature minor has the capacity and competence to consent to the study.
- 4. Meeting one or more UHR for psychosis groups (as defined in Table 1).

902 Young people seeking help via headspace centres are routinely screened using the HEADSS

assessment, and as clinically appropriate, an additional screening tool will be used by clinicians which will help them determine the UHR status of their clients. This tool is the Prodromal Questionnaire-16 (PQ-16)(144). Those who score 6 or more positive symptoms on the PQ-16 will be assessed using the CAARMS(142) and SOFAS(148) to determine UHR status. A cut-off score of 6 on the PQ-16 screening tool has previously been found to identify UHR+ cases with high sensitivity (87%) and specificity (87%) (144) and has also been found to identify a more enriched sample for psychosis risk (146). This will not apply at the PACE clinic as all clients have already been assessed as UHR + through clinician administered CAARMS (as part of standard clinical entry).

Table 1: Operationalised UHR intake criteria

913 914

903

904

905 906

907

908 909

910

911

912

1. Group 1: Vulnerability Group

Family history of psychosis in first degree relative OR Schizotypal Personality Disorder (as defined by DSM IV) in identified patient

AND

Drop in Functioning:

Recency: Change in functioning occurred within last year

Impact: SOFAS score at least 30% below previous level of functioning and sustained for at least one month.

OR

Sustained low functioning:

Recency: For the past 12 months or longer

Impact: SOFAS score of 50 or less.

915 916

2. Group 2: Attenuated Psychotic Symptoms Group

2a) Subthreshold intensity:

Intensity: Global Rating Scale Score of 3-5 on *Unusual Thought Content* subscale, 3-5 on *Non-Bizarre Ideas* subscale, 3-4 on *Perceptual Abnormalities* subscale and/or 4-5 on *Disorganised Speech* subscales of the CAARMS

Frequency: Frequency Scale Score of 3-6 on *Unusual Thought Content, Non-Bizarre Ideas, Perceptual Abnormalities* and/or *Disorganised Speech* subscales of the CAARMS Duration: symptoms present for at least one week

Recency: symptoms present in past year

2b) Subthreshold frequency:

Intensity: Global Rating Scale Score of 6 on *Unusual Thought Content* subscale, 6 on *Non-Bizarre Ideas* subscale, 5-6 on *Perceptual Abnormalities* subscale and/or 6 on *Disorganised Speech* subscales of the CAARMS

Frequency: Frequency Scale Score of 3 on *Unusual Thought Content, Non-Bizarre Ideas,, Perceptual Abnormalities* and/or *Disorganised Speech* subscales of the CAARMS Recency: symptoms present in past year

917 3. Group 3: BLIPS Group

Intensity: Global Rating Scale Score of 6 on *Unusual Thought Content* subscale, 6 on *Non-Bizarre Ideas* subscale, 5 or 6 on *Perceptual Abnormalities* subscale and/or 6 on *Disorganised Speech* subscales of the CAARMS

Frequency: Frequency Scale Score of 4-6 on *Unusual Thought Content, Non-Bizarre Ideas, Perceptual Abnormalities* and/or *Disorganised Speech* subscales

Duration: Symptoms present for less than one week and spontaneously remit on every occasion.

Recency: symptoms present in past year

918

919 **6.6. Exclusion Criteria**

- 920 Potential participants who meet any of the following criteria will not be eligible for
- participation in this study. Applications for individual protocol waivers will be considered on
- a case-by-case basis as detailed in Section 6.4.
- 923 Exclusion criteria consist of:
- 924 1. Past history of a psychotic episode of one week or longer, whether treated with
- 925 antipsychotic medications or not.
- 926 2. Attenuated psychotic symptoms only present during acute intoxication.
- 927 3. Organic brain disease known to cause psychotic symptoms, e.g. temporal lobe epilepsy.
- 928 4. Any metabolic, endocrine or other physical illness, e.g. thyroid disease, with known
- 929 neuropsychiatric consequences.
- 930 5. Diagnosis of a serious developmental disorder, e.g. Severe Autism Spectrum Disorder.
- 931 6. A documented history of developmental delay or intellectual disability.
- 932 7. Previous or current SCID diagnosis of bipolar disorder I.

- 933 Previous or current use of antipsychotic or antidepressant medication is not an exclusion 934 criterion. In the case of current antipsychotic or antidepressant use, we will taper and cease this at entry to the study. This is consistent with clinical guidelines because antipsychotics 935 936 are not indicated for the UHR population (147, 148) and antidepressants in young people are 937 recommended only for those with severe depression, with psychosocial interventions 938 recommended for those with mild-moderate depression (149). Most UHR cases who suffer 939 from depression have mild-moderate rather than severe depression (143, 150). If they 940 develop severe depression during the course of the study they are likely to meet the 941 discontinuation criterion of risk to self and be commenced on antidepressant medication.
- 942 6.7. Participants Restrictions

946 947

948

949

950

951

952

953

954

955

956

957

958

959

960

961

962

963

964 965

In Steps 1 and 2 antidepressants will not be permitted. The use of antipsychotics or mood stabilisers is not permitted for the duration of the study (24 months).

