step will produce resolution of the current clinical phenotype in around 50% of participants, and thereby enrich the remaining sample for psychosis risk and functional impairment for randomisation in subsequent steps (57, 58). We also expect this to help retention of participants as drop outs have tended to occur early in previous UHR trials (93). Participants who respond to Step 1 (see below for definition of response) will be randomised to SPS monthly sessions v Monitoring at 3, 6, 9 and 12 months post entry to Step 1.

Monitoring will consist of the research assistant conducting a research assessment in addition to the clinician making contact with the participant, either by phone or in person, in order to monitor mental state and risk and to assess whether there has been any mental health deterioration which would indicate a need for change in clinical management (e.g., referral to a new service or need to re-engage with headspace or Orygen).

Step 2: CBCM vs SPS: Participants who do not respond (estimated at 50%) to Step 1 will be randomised to one of two treatment groups for 18 weeks (4.5 months): A more intensive psychosocial intervention (cognitive behavioural case management: CBCM) versus SPS. This design will test the potential benefit of a more intensive psychosocial intervention compared to extending the more basic intervention provided in Step 1 (SPS). It is not yet clear whether CBT, the primary component of CBCM, offers benefits over and above SPS. It is possible that non-responders to Step 1 (6 weeks of SPS) have simply not received the SPS intervention for long enough (i.e., the "dose" of SPS has not been sufficient to achieve symptom response and functional improvement). Extending SPS to a total of 6 months duration in Step 2 will test this possibility, as well as the potential benefit of introducing a more intensive psychotherapy in the form of CBCM. Research assistants conducting the research assessments will be blind to treatment allocation. This step will test an intervention that targets a key putative mechanism for psychosis vulnerability and risk: the psychological mechanism of dysfunctional cognitive biases.

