1877 1878 1879 1880	Data quality will be ensured by performing data entry checks for consistency between raw data, the eCRF, and the data entry database. These checks will be performed during data entry so that discrepancies can be resolved immediately. This will be performed remotely through electronic means and in-person at each site.		
1881 1882 1883 1884 1885	Each site will maintain a record of all personnel involved in the study as delegated by the PI. In consultation with the central coordinating centre, Orygen, each trial centre will ensure that appropriate training is provided to study personnel, and that any new information of relevance to the performance of this study is forwarded to the staff involved. All training will be documented and form part of the study essential documents.		
1886	14. Statistical Methods		
1887 1888 1889 1890 1891 1892	14.1. Methodology The primary analysis is to compare the two Step 2 treatments on the 6-month Global Functioning: Social and Role Scale score (130) using analysis of covariance with the baseline Global Functioning: Social and Role Scale score as the covariate. The treatment options in Steps 2 and 3 correspond to 4 treatment regimes for the non-responders. Comparing fluoxetine and placebo from Step 3 is equivalent to collapsing these regimes into two		
1893 1894	groups. A secondary analysis will be to compare these two groups using ANCOVA in terms of 12-month Global Functioning: Social and Role Scale score. Comparing the different		

treatment regimes will also be considered. Survival analysis will also be used for comparison

1901 1902		analysis in the EXPECT sub study: Participants' demographic characteristics and belief	
1903 1904 1905 1906 1907	about the degree of risk will be described quantitatively. Their beliefs regarding children's autonomy in regards to being identified as at-risk, as well as regarding interventions will be examined using thematic analysis. Their responses with regards to their experience of their son/daughter being identified as being at-risk will be examined using interpretative		
1908	prieric	omenological analysis.	
1909	14.2.	Analysis Populations	
1910		14.2.1. Efficacy	
1911	Intent	ion to Treat (ITT) analysis will be conducted.	
1912		14.2.2. Safety Analysis	
1913 1914		afety population will consist of all participants who were randomised and received at one SPS session in Step 1 and had at least one post-baseline assessment.	

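### Section 6.2 gives detectable effects of 0.18 and 0.29 with no metric, and its stated inputs do not return both figures; they should be restated as standardised mean differences with every assumption declared

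*Protocol*

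**What the plan says.** Section 6.2 (Sample Size and Power) starts from 500 entrants, 50% non-response to Step 1 and 20% drop-out: "response rate in Step 1, an entry sample size of 500, a drop-out rate of 20% and hence a step" 2 sample of 200. From that number it says "we will be able to detect a fairly small effect size (0.18 in a parallel cell" "design) with a power of 80% and significance level of .05 by the end of Step 2". For Step 3 it applies a further 50% non-response and 20% loss: "drop-out rate will result in n=80 in Step 3 which will be sufficient to detect a clinically" "important medium effect size (0.29) for comparing the two interventions with a power of" 80% at .05.

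The comparison is between two arms: in the description of Step 2 in section 5, non-responders are "randomised to one of two treatment groups for 18 weeks (4.5 months"). Section 14.1 (Methodology) fixes the primary analysis: "Functioning: Social and Role Scale score (130) using analysis of covariance with the baseline" score as covariate.

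Nowhere does the protocol say whether 0.18 and 0.29 are standardised mean differences, Cohen's f or something else. It also gives no sidedness, allocation ratio, SD, difference in scale points or assumed correlation between baseline and six-month scores.

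**The concern.** For a two-group comparison of means, many readers take an unlabelled effect size to be a standardised mean difference (SMD). On that reading the trial would be sensitive to a benefit of CBCM over SPS of less than a fifth of an SD, which 100 per arm cannot deliver at 80% power. On the most favourable reading that fits the numbers, the same claim means about 0.36 SD.

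The difference matters most if the primary comparison is null. That outcome is plausible: section 4.1 reports an earlier trial in which supportive therapy did as well as CBT in this population. Someone relying on section 6.2 could then conclude that the trial was built to exclude small benefits, which it was not.

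**Working it through.** **Inputs.** From section 6.2: n=200 (Step 2), n=80 (Step 3), alpha .05, power 80%. From section 5: two arms. From section 14.1: ANCOVA on the baseline score. My assumptions, because the text is silent: 1:1 allocation, two-sided test (one-sided also tried), and correlation rho between baseline and outcome from 0 to 0.7.

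**Participant flow.** 500 × 0.5 × 0.8 = 200, and 200 × 0.5 × 0.8 = 80. Both sample sizes reproduce.

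**Detectable effect.** For total N with equal arms, SMD = (z for alpha + z for power) × √(4/N). Two-sided, the sum is 1.960 + 0.842 = 2.802.

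- N=200: 2.802 × √(4/200) = 0.396 (exact t: 0.398).
- N=80: 2.802 × √(4/80) = 0.626 (exact t: 0.634).

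For two equal groups Cohen's f is half the SMD. Adjusting for baseline multiplies the detectable effect by √(1 − rho²).

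**Trying to reproduce 0.18 and 0.29** (80% power):

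| Reading | n=200 | n=80 | Returns 0.18 and 0.29? |
|---|---|---|---|
| SMD, two-sided, no covariate | 0.398 | 0.634 | Neither |
| SMD, two-sided, 200 and 80 read as per arm | 0.280 | 0.443 | Neither |
| Correlation coefficient (Fisher z), two-sided | 0.197 | 0.309 | Neither |
| f, two-sided, no covariate | 0.199 | 0.317 | Neither |
| f, one-sided, no covariate | 0.176 | 0.280 | First only |
| f, two-sided, numbers before drop-out (250 and 100) | 0.178 | 0.283 | First only |
| f, two-sided, rho = 0.40 | 0.1825 | 0.2907 | Both, rounded |
| f, two-sided, rho = 0.42 | 0.181 | 0.288 | Both, rounded |

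Only f combined with a correlation of about 0.4 returns both. Solved separately, 0.18 implies rho = 0.43 and 0.29 implies rho = 0.40. Neither the metric nor the correlation is in the protocol.

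**Power at the stated figures.**

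- Read as SMDs, two-sided: about 25% for 0.18 at n=200 and about 25% for 0.29 at n=80. Reaching 80% needs 2 × (2.802/0.18)², or 485 per arm (970 in all), and 2 × (2.802/0.29)², or 187 per arm (374 in all).
- Correlation that ANCOVA would need to rescue the SMD reading: √(1 − (0.18/0.398)²) = 0.89 and √(1 − (0.29/0.634)²) = 0.89.
- Read as f with no covariate gain: 72% and 73%.
- Read as f with rho = 0.42: 79.7% and 80.6%. With rho = 0.5: 83% and 84%.

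**Detectable SMD under the planned ANCOVA** (n=200 / n=80): rho 0.3, 0.38 / 0.61; rho 0.4, 0.365 / 0.58; rho 0.5, 0.345 / 0.55; rho 0.7, 0.28 / 0.45. Doubling the printed figures as f gives 2 × 0.18 = 0.36 and 2 × 0.29 = 0.58.

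**If 200 and 80 are entrants.** A further 20% loss leaves 200 × 0.8 = 160 and 80 × 0.8 = 64 with an outcome. The detectable SMDs are then 0.45 and 0.71 with no covariate (exact t: 0.446 and 0.712).

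**The case against.** The strongest reply is that nothing has been shown to be miscalculated. The protocol never calls the figures SMDs. Its own labels suit Cohen's f: on the usual benchmarks 0.29 is near medium for f (0.25) but well short of medium for an SMD (0.5). A single plausible correlation reproduces both numbers, ANCOVA is the planned analysis, and the synopsis says that earlier UHR data informed the sample size. The correlation may be recorded in an SAP that is not at hand.

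Much of this stands. A reader might infer that the calculation is wrong and that 0.40 and 0.63 are the true figures. The document does not support that: those values assume no gain from the baseline covariate, whereas the planned analysis uses one. Nor does it support calling the description of 0.18 as fairly small an error. If f was meant, the equivalent SMD of 0.36 lies between the conventional small (0.2) and medium (0.5).

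A reader might also infer that only 160 and 64 will be analysed. Section 6.2 takes the 20% off before reaching 200 and speaks of power at the end of Step 2, so 200 and then 80 participants with outcomes is a coherent reading. Section 4.4, which gives the Step 2 size as at least 200, leaves room for the other.

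The reply does not settle the central point. The correlation of about 0.4 is back-solved, so it explains the figures without confirming them. An SAP could supply it, but the protocol already prints a specific power claim that its own stated assumptions do not deliver. A null result would indeed be judged mainly from its confidence interval, which limits the harm without making the statement correct.

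**Conclusion.** The point holds as a fault in how the power claim is stated. Section 6.2 gives 80% power for 0.18 and 0.29 without a metric, sidedness or baseline correlation, and its inputs alone do not return both figures on any scale tried. As SMDs the claim fails clearly (about 25% power, or a correlation near 0.89). As Cohen's f it is met only with an undeclared correlation of about 0.4; otherwise power is 72% and 73%. In SMD terms the design detects about 0.40 and 0.63 with no covariate gain, or about 0.36 and 0.58 with that correlation.

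These results assume 1:1 allocation, a two-sided .05 test, and 200 and 80 participants with an outcome. They do not show a computing error or that the sample size must change.

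**What to change.** Rewrite the power statement in section 6.2 as follows.

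- Give the detectable effects as SMDs, with two-sided .05, 80% power and 1:1 allocation stated (or the actual sidedness and ratio, with the figures recomputed): 0.40 at n=200 and 0.63 at n=80 with no covariate gain.
- If credit is taken for ANCOVA, declare the assumed baseline correlation and its source. At about 0.4 the figures are 0.36 and 0.58.
- If Cohen's f was the metric used, say so and give the SMD beside it. A difference in scale points would help, once an SD is declared.
- State whether 200 and 80 are participants entering the step or participants with an outcome. Only if they are entrants who lose a further 20%, quote 0.45 and 0.71 (no covariate).

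The cost is one paragraph and a less favourable-looking figure. No extra patients are needed, and the endpoint, analysis and conduct are unchanged.
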